S-600918 Shionogi Clinical Study Protocol: 1812VA323 Version 3 10 Sep 2020

NCT #: NCT04110054

Study Protocol: 1812VA323

Study Title:	A Phase 2b, multicenter, randomized, double-blind, placebo-controlled, parallel-group, dose-selection study of S-600918 in patients with refractory chronic cough
Study Number:	1812VA323
EudraCT No:	2019-002283-27
IND No.:	144078
Study Phase:	2b
Product Code Number:	S-600918
Sponsor*:	Shionogi & Co., Ltd. [name]
Sponsor*:	Shionogi Inc. [name]
Sponsor*:	Shionogi B.V. [name]
Sponsor Contact:	Shionogi Inc. [name] TEL: Shionogi Inc. [name] TEL:

Protocol Version Issue Date:

Version 1 (Original):	04 Sep 2019
Version 2:	07 Nov 2019
Version 3:	10 Sep 2020

^{*} The study sponsor may be one or more of the above companies. Throughout the protocol, the term "sponsor" represents the various legal entities identified as "Sponsor" in the Study Administrative Structure in the protocol. The above companies are referred to as Shionogi.

Confidentiality Statement

Shionogi

10 Sep 2020

This document and the information contained herein or attached hereto ("Confidential Material") are confidential and proprietary to Shionogi. This Confidential Material should only be viewed by those individuals or companies that have been given prior authorization to do so by Shionogi ("Authorized Users"). This Confidential Material should not be made available in any form to any person or company, other than the Authorized Users and their respective employees or associates on a need-to-know basis, without the written consent from Shionogi.

SYNOPSIS

Study Title:

A Phase 2b, multicenter, randomized, double-blind, placebo-controlled, parallel-group, dose-selection study of S-600918 in patients with refractory chronic cough

Study Number: 1812VA323

Study Phase: 2b

Primary Objective: To determine the optimal dose of S-600918 in patients with refractory chronic cough by evaluating the change from baseline in 24-hour cough frequency (coughs per hour) with S-600918 compared with placebo

Secondary Objectives:

- To compare the efficacy of S-600918 to that of placebo in patients with refractory chronic cough based on the following measurements:
 - Number of coughs per hour while awake
 - Number of coughs per hour while asleep
 - Severity of cough as assessed on the Visual Analog Scale (VAS)
 - Leicester Cough Questionnaire (LCQ)
 - International Consultation on Incontinence Modular Questionnaire-Short Form (ICIQ-SF)
 - Short-Form (36) Health Survey (SF-36), version 2
 - Patient Global Impression of Change (PGIC)
- To evaluate the safety of S-600918 in patients with refractory chronic cough.
- To assess the pharmacokinetics (PK) of S-600918 and its metabolite (S-600918 acyl glucuronide) in patients with refractory chronic cough.

Study Design:

This study will be conducted as a multinational, multicenter, randomized, double-blind, placebo-controlled, parallel-group study. A total of approximately 372 patients with refractory chronic cough are planned to be treated in Japan, Europe, and the United States.

This study will include 3 periods: a screening period, a treatment period, and a follow-up period. After obtaining informed consent, patients who meet screening criteria at Visit 1 will be enrolled in the study, and a cough monitor will be applied to each patient. Patients will be instructed to remove the cough monitor after 24 hours and to return the cough monitor to the study site within 2 days after completing the cough monitor recording. At least 17 days after Visit 1, patients will return for Visit 2, at which time screening will continue and a cough monitor again will be applied to each patient for 24 hours. Patients will return 1 day later for Visit 3. Patients who continue to meet screening criteria at Visit 3 will be randomized in a 1:1:1:1 ratio (93 patients per treatment group) to study treatment with S-600918 50 mg, S-600918 150 mg, S-600918 300 mg, or placebo. Randomization will be stratified by region (Japan, Europe, or the United States) and hourly cough count based on the 24-hour cough

count recording at Visit 1 (≥30 coughs/hour or <30 coughs/hour) and will be performed by Interactive Response Technology (IRT). Following randomization, patients will take the first dose of study drug while at the study site. Study drug will be taken orally once daily for 28 days. Patients will be followed for 14 days after the last dose of study drug.

Study Population:

Patients with refractory chronic cough

Criteria for Inclusion and Exclusion:

Inclusion Criteria

Patients who meet the following criteria at the specified visit(s) will be included in the study provided no exclusion criterion is met:

	Inclusion Criteria	Visit 1	Visit 2	Visit 3
1.	Willing to comply with all study procedures.	$\sqrt{}$	$\sqrt{}$	
2.	Capable of giving signed informed consent. (Informed consent will be obtained in accordance with local requirements.)	√		
3.	Male or female outpatient ≥ 18 to ≤ 80 years of age at the time of signing the informed consent form.	$\sqrt{}$		
4.	Has refractory chronic cough lasting for at least 1 year prior to Visit 1, defined as:			
	• insufficient improvement in cough after treatment for the underlying condition(s) causing the cough OR	$\sqrt{}$		
	 unexplained cough for which an underlying condition has not been determined. 			
5.	With severity of cough assessed as ≥40 mm on the Visual Analog Scale (VAS) at both Visit 1 and Visit 2.	$\sqrt{}$	$\sqrt{}$	
6.	With cough count ≥10 times per hour based on the 24-hour cough count recording at Visit 1. (Results will be available by Visit 2; no calculation is necessary.)		V	
7.	If female, agreement to use one of the following contraceptive methods from screening until 14 days after the last dose of study drug UNLESS the patient is surgically sterile by hysterectomy, bilateral oophorectomy, and/or bilateral salpingectomy or tubal ligation with appropriate documentation of such surgery or postmenopausal (defined as at least 12 months of spontaneous amenorrhea in women >45 years of age):	√		

S-600918 Shionogi Clinical Study Protocol: 1812VA323 Version 3 10 Sep 2020

 Progestogen-only oral hormonal contraception (where inhibition of ovulation is not the primary mode of action), male or female condom with or without spermicide, cap, diaphragm, or sponge with spermicide. 		
The contraceptive methods listed above are the minimum required per protocol. Other accepted methods include combination estrogen- and progesterone-containing contraceptives, implanted devices (such as intrauterine devices [IUDs]), and injectable contraceptives.		

Exclusion Criteria

Patients who meet any of the following criteria at the specified visit(s) will be excluded from the study:

Exclusion Criteria	Visit 1	Visit 2	Visit 3
1. Missing an entry in patient electronic diary (eDiary) for the number of coughs on more than 30% of the days from day of Visit 1 up to day of Visit 2. (Entries will be assessed at Visit 2.)		V	
2. Failure to obtain the cough count recording on the cough monitor at Visit 1 or Visit 2 for any reason, including device malfunction, based on initial assessment at study site.			
 Assessment for Visit 1 will be completed prior to Visit 2. If recording at Visit 1 is assessed as failed, the recording may be repeated (see Section 8.1 for details). 	$\sqrt{}$		V
• Assessment for Visit 2 will be completed at Visit 3. If recording at Visit 2 is assessed as failed, the recording may be repeated (see Section 8.3 for details).			
3. Currently smokes (including, but not limited to e-cigarettes, smokeless cigarettes, and vaping) or uses any inhalational agents (including, but not limited to marijuana) that are potential irritants or has smoked or used any inhalational agents that are potential irritants in the 1 year prior to Visit 1 or has a smoking history of ≥20 pack-years (Pack years = [Number of cigarettes per day/20] × (Number of years of smoking]).	.		

S-600918 Clinical Study Protocol: 1812VA323 Version 3 Shionogi 10 Sep 2020

4.	Produces a significant amount of sputum suggestive of infection, bronchiectasis, chronic bronchitis, etc.	$\sqrt{}$	$\sqrt{}$	$\sqrt{}$
5.	In the 4 weeks prior to Visit 1 or during screening, history of infection in the upper or lower respiratory tract or a significant change in lung function or a pulmonary condition based on the judgment of the investigator.	V	V	V
6.	Has chronic obstructive pulmonary disease (COPD) or, as defined in the Global Initiative for Asthma (GINA) 2019, has uncontrolled asthma symptoms (excluding cough) [a].	V		
7.	Has a clinically unstable medical condition, including cardiac disease (eg, atrial fibrillation, symptomatic bradycardia, and active myocardial ischemia), hypertension, respiratory disease, biliary tract disease, hypothyroidism, renal disease, adrenocortical insufficiency, or any other medical condition that, in the opinion of the investigator, will interfere with study participation or assessment of efficacy and safety.	V	V	
8.	Has history of malignancy ≤5 years prior to Visit 1 (unless nonmelanoma skin cancer).	$\sqrt{}$		
9.	Has history of or current bipolar disorder, schizoaffective disorder, schizophrenia, or major depressive disorder [b], or, based on the judgment of the investigator, has other psychiatric symptoms that may interfere with study procedures.	V		
10	. Has history of severe drug allergy (shock, anaphylaxis, or angioedema).	$\sqrt{}$		
11.	. Has history of alcohol or drug abuse in the 1 year prior to Visit 1 or uses any form of marijuana or illicit drugs.	V		
12.	With alanine aminotransferase (ALT) or aspartate aminotransferase (AST) >2.0 times the upper limit of the normal reference range (× ULN) or total bilirubin >1.5 × ULN. (ULN is as determined by the central laboratory. Results will be available by Visit 2.)		V	
13.	. With serum creatinine $>1.5 \times ULN$. (ULN is as determined by the central laboratory. Results will be available by Visit 2.)		$\sqrt{}$	

Shionogi 10 Sep 2020

14. With positive serological test for human immunodeficiency virus (HIV) antigen or antibody. (Results will be available by Visit 2.)		√	
15. With positive serological test for hepatitis B virus surface antigen. (Results will be available by Visit 2.)		√	
16. With positive serological test for hepatitis C virus RNA. (This test is required only if patient has positive serological test for hepatitis C virus antibody. Results will be available by Visit 2.)		V	
17. With systolic blood pressure >160 mm Hg or diastolic blood pressure >90 mm Hg.	V	√	√
18. With clinically significant abnormal electrocardiogram (ECG) based on the judgment of the investigator.	√	√	
19. With a ratio of forced expiratory volume in 1 second (FEV ₁) to forced vital capacity (FVC) less than 60% at Visit 1.			
COVID-19—related Measure: With a ratio of forced expiratory volume in 1 second (FEV ₁) to forced vital capacity (FVC) less than 60% based on spirometry conducted anytime in the prior calendar year [c].	V		
20. With any finding on a chest x-ray or chest computed tomography (CT) scan (performed not more than 1 year [12 months] prior to Visit 1 after onset of chronic cough at Visit 1) that could be considered the cause of chronic cough or indicative of lung disease. (If a chest x-ray or chest CT scan needs to be performed, results will be available by Visit 2.) (Note: Patients with abnormal chest image findings not considered to be the cause of chronic cough are eligible to participate.)	V	V	
21. Previously received S-600918.	V		
22. Treated with a biological drug for asthma in the 3 months prior to Visit 1 or previously received bronchial thermoplasty.	√		

S-600918 Clinical Study Protocol: 1812VA323 Version 3 Shionogi 10 Sep 2020

23. Treated with an angiotensin-converting-enzyme (ACE) inhibitor in the 3 months prior to Visit 1, being treated with an ACE inhibitor at Visit 1, or planned to be treated with an ACE inhibitor at any time from Visit 1 to the end-of-study (EOS) assessments at Visit 7.	V	V	√
24. Received an investigational drug in the 3 months prior to Visit 1 or planned to receive another investigational drug at any time from Visit 1 to the EOS assessments at Visit 7.	V	V	V
 25. Being treated with the following therapy at Visit 1 or planned to be treated with the following therapy at any time from Visit 1 to the EOS assessments at Visit 7: Pregabalin, gabapentin, and tricyclic antidepressants Biological products for asthma treatment (eg, omalizumab) Baclofen Sitagliptin P-glycoprotein (P-gp) inhibitors (specifically, cyclosporine, erythromycin, itraconazole, and ketoconazole [This criterion does not apply to topical formulations of these drugs, if any.]) Breast cancer resistance protein (BCRP) inhibitors (specifically, cyclosporine [This criterion does not apply to topical formulations of this drug, if any.]) Organic anion transporting polypeptide (OATP)1B1/1B3 inhibitors (specifically, cyclosporine and gemfibrozil [This criterion does not apply to topical formulations of these drugs, if any.]) Digoxin or methyldigoxin 	√	√	~
26. Refusal to discontinue the following therapy at			
Visit 1 to the EOS assessments at Visit 7:			
 Drugs with an antitussive action alone or in combination with other drugs 	$\sqrt{}$	$\sqrt{}$	$\sqrt{}$
Herbal medicines with an antitussive action			
 First-generation (sedating) antihistamines (other than topical products) 			

S-600918 Shionogi

Clinical Study Protocol: 1812VA323 Version 3 10 Sep 2020

 Non-drug therapies for cough relief, including cough suppressant speech therapy UNLESS used as specified under "Restricted Therapy" (Section 6.2.2): Sleep-inducing drugs Drugs with an expectorant action Steroids (other than nasally administered steroids and other topically administered steroids) Drugs having an effect on gastrointestinal (GI) motility or GI acid reflux, including proton pump inhibitors, prokinetic drugs, and histamine H₂ receptor antagonists Anti-allergics (other than first-generation antihistamines and topical products) (histamine H₁ receptor antagonists, thromboxane A2 synthase inhibitors, thromboxane receptor antagonists, thromboxane receptor antagonists, Th2 cytokine blockers, mediator release inhibitors) Long-acting beta agonists, long-acting muscarinic antagonists, and bronchodilators other than short-acting beta-2 agonists (eg, methylxanthines and phosphodiesterase [PDE] inhibitors, etc.) Macrolide antibiotics (other than erythromycin) Oral anticholinergics Immunotherapy for allergic disease 				
27. If female, pregnant or trying to become pregnant or lactating.	$\sqrt{}$	$\sqrt{}$	$\sqrt{}$	
28. Considered ineligible to participate in the study	.1	.1	.1	
for any other reason, based on the investigator's judgment.	٧	٧	V	

[a] As guidance regarding uncontrolled asthma symptoms, in the 2 to 3 months prior to Visit 1, an increase or decrease in the dose of an asthma controller drug AND, in the 4 weeks prior to Visit 1, at least 3 of the following: daytime symptoms of asthma more than twice per week, any night waking due to asthma, any activity limitation due to asthma, or use of asthma reliever more than twice per week.

- [b] History of major depressive disorder is exclusionary only if there was a formal psychiatric diagnosis of major depressive disorder and the patient received antidepressant treatment. A vague history of having been depressed in the past is not exclusionary.
- [c] If there are no spirometry data in the prior calendar year, spirometry is required at Visit 1. Assess whether the possible benefit from participating in the study will outweigh the risk of conducting spirometry. If the benefit-risk assessment is positive, perform spirometry in accordance with local guideline(s). If the benefit-risk assessment is negative, stop screening that patient.

Study Drug, Dose, and Mode of Administration:

Test Drug - S-600918 50-mg tablets administered orally once daily at a dose of 50 mg, 150 mg, or 300 mg.

Control Drug - Placebo matching S-600918 50-mg tablets administered orally once daily.

Timing of Study Drug Administration and Cough Monitoring:

Patients will take study drug orally once daily (preferably in the morning) with or without food on all treatment days except on the day of Visit 4.

For the day of Visit 4, patients will be instructed to come to the study site in the morning without taking the study drug that day. After patient completion of specified questionnaires and instruments on the electronic tablet, a blood sample will be collected for PK analysis and then the patient will take that day's dose of study drug.

The 24-hour cough monitor recording at Visit 4, Visit 5, and Visit 6 will be started within \pm 3 hours from the start time of the cough monitor recording at baseline (Visit 2).

Duration of Treatment:

28 days

Concomitant Therapy:

Enrollment of patients being treated with or planned to be treated with specific therapy at any time at Visit 1 to the EOS assessments at Visit 7, as detailed in Exclusion Criteria #23, 24, and 25 is not permitted. Enrollment of patients who refuse to discontinue specific therapy at Visit 1 to the EOS assessments at Visit 7, as detailed in Exclusion Criterion #26, is not permitted.

The on-demand use of short-acting beta-2 agonists (SABAs) is discouraged during each of the 24-hour periods while patients are wearing a cough monitor. All patients must be specifically asked about the use of SABAs at Visit 1 and while wearing the cough monitor when reviewing prior and concomitant therapies (as applicable) at Visit 2, Visit 3, Visit 5, Visit 6, Visit 7, and/or, if applicable, the Early Discontinuation Visit.

Efficacy Assessments:

Efficacy will be assessed based on cough monitor recordings of cough counts and questionnaires or instruments used in studies in this patient population, including the

VAS to assess severity of cough, LCQ, ICIQ-SF, SF-36, and PGIC. The patient will complete the questionnaires and instruments using an electronic tablet and an eDiary.

Pharmacokinetic Assessments:

Plasma concentrations of S-600918 and its metabolite (S-600918 acyl glucuronide) will be determined.

Safety Assessments:

- Adverse events
- Physical examinations
- Clinical laboratory tests
- Blood pressure and pulse rate
- ECGs

Statistical Methods:

Efficacy Analyses

The primary endpoint is the ratio of the number of coughs per hour in 24 hours (based on cough counts recorded by the cough monitor) after administration of study drug for 4 weeks to that at baseline (Visit 2). A mixed effect model will be applied to the common logarithm of the ratio of the number of coughs per hour in 24 hours at Visit 4, Visit 5, and Visit 6 to that at baseline as response. This model will contain treatment group, week, and the interaction between treatment group and week as fixed effect; patient as random effect; and region and the common logarithm of the frequency of coughs per hour in 24 hours at baseline as covariates. The covariance structure will be determined to be unstructured. The dose-response relationship will be evaluated by a comparison of each dose level of S-600918 to placebo.

Secondary endpoints include a reduction from baseline in the number of coughs per hour in 24 hours by $\ge 30\%$, $\ge 50\%$, and $\ge 70\%$; the ratio of the number of coughs per hour while awake after administration of study drug for 4 weeks to that at baseline and a reduction by $\ge 30\%$, $\ge 50\%$, and $\ge 70\%$; the ratio of the number of coughs per hour while asleep after administration of study drug for 4 weeks to that at baseline; the change from baseline in weekly cough severity as assessed on the VAS (electronic tablet); the change from baseline in daily cough severity as assessed on the VAS through Day 7 (eDiary); the change in LCQ and achievement of an increase (ie, improvement) of ≥ 1.3 points; the change in ICIQ-SF; the change in SF-36; and the PGIC.

The proportion of patients who achieved a reduction from baseline in the number of coughs per hour in 24 hours by $\ge 30\%$, $\ge 50\%$, and $\ge 70\%$ after administration of study drug for 4 weeks will be compared between each dose level of S-600918 and placebo by applying the Cochran-Mantel-Haenszel test with strata by region (Japan, Europe, or the United States) and cough count at baseline (≥ 30 coughs/hour or ≤ 30 coughs/hour).

An analysis method similar to that used to determine the ratio of the number of coughs per hour in 24 hours will be applied to the ratio of the number of coughs per hour while awake to that at baseline; change in weekly cough severity as assessed on the VAS (electronic tablet); change in daily cough severity as assessed on the VAS through

Day 7 (eDiary); change in LCQ; change in ICIQ-SF; and change in SF-36. Also, for the number of coughs per hour while awake, the cough severity as assessed on the VAS, and the LCQ, the proportion of patients who achieved a certain level of reduction will be analyzed using the same analysis method applied to the number of coughs per hour in 24 hours. The van Elteren test with strata by region (Japan, Europe, or the United States) and cough count at baseline (≥30 coughs/hour or <30 coughs/hour) will be applied to compare the assessments of PGIC at each dose level of S-600918 to placebo.

Safety Analyses

The number and percentage of patients with treatment-emergent adverse events (TEAEs) will be summarized overall and by the Medical Dictionary for Regulatory Activities (MedDRA) system organ class and preferred term for all TEAEs and those considered to be related to treatment for each treatment group. Summary statistics for laboratory tests, blood pressure, and pulse rate at each planned observation point and the change from baseline at each planned observation point will be calculated by treatment group. A categorical analysis of qualitative laboratory test values (urinalysis) and qualitative ECG values at each planned observation point will be performed by treatment group.

Study Duration:

The study duration for each patient is approximately 8 to 10 weeks (screening, 18 to 28 days; treatment, 28 days; and follow-up, 14 days).

Date of Original: 04 Sep 2019

Date of Latest Amendment: 10 Sep 2020

TABLE OF CONTENTS

SY	NOPSI	S	3
TA	ABLE O	F CONTENTS	13
LI	ST OF I	N-TEXT TABLES	17
LI	ST OF I	N-TEXT FIGURES	17
LI	ST OF A	ABBREVIATIONS AND DEFINITIONS OF TERMS	18
C	OVID-19	PANDEMIC	21
1.	INTR	ODUCTION	23
	1.1	Disease Concept and Treatments	23
	1.2	S-600918	23
	1.2	.1 Rationale	23
	1.2	.2 Clinical Summary	24
	1.3	Rationale for the Study	28
2.	STUI	DY OBJECTIVES	29
	2.1	Primary Objectives	29
	2.2	Secondary Objectives	29
3.	INVE	STIGATIONAL PLAN	30
	3.1	Overall Study Design and Plan	30
	3.2	Rationale for Study Design and Control Group	31
	3.3	Study Duration	32
	3.3	.1 Study Duration in Individual Patients	32
	3.3	.2 Planned Study Duration for the Study	32
	3.3	.3 Study End	32
4.	STUI	DY ENROLLMENT AND WITHDRAWAL	33
	4.1	Study Population	33
	4.2	Inclusion Criteria	33
	4.3	Exclusion Criteria	34
	4.4	Screen Failures	39
	4.5	Withdrawal of Patients from the Study and Discontinuation of Study Drug .	39
	4.5	.1 Withdrawal of Patients from the Study	39

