9.10.3.1 Analysis of Primary Endpoint

A mixed effect model will be applied to the common logarithm of the ratio of the number of coughs per hour in 24 hours at Visit 4, Visit 5, and Visit 6 to that at baseline as response. This model will contain treatment group, week, and the interaction between treatment group and week as fixed effect; patient as random effect; and region and the common logarithm of the frequency of coughs per hour in 24 hours at baseline as covariates. The covariance structure will be determined to be unstructured. When the mixed model with unstructured covariance fails in convergence, compound symmetry will be applied as covariance structure. Under this model, the ratio of the number of coughs per hour in 24 hours after 4 weeks of administration to that at baseline will be compared between each dose level of S-600918 and placebo. The dose-response relationship will be evaluated by a comparison of each dose level of S-600918 to placebo. This analysis will be performed for the FAS and the PPS.

Summary statistics for the number of coughs at each visit will include the geometric mean and its 95% confidence interval.

A subgroup analysis based on the combination of region and cough count at baseline will be performed and will include the following subgroups: region (Japan, Europe, and the United States) and cough count at baseline (\geq 30 coughs/hour and <30 coughs/hour). Another subgroup analysis based on the combination of region and cough count at screening (Visit 1) will be performed and will include the following subgroups: region (Japan, Europe, and the United States) and cough count at screening (\geq 30 coughs/hour or <30 coughs/hour).

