8.1.1. Primary Analysis

The null hypotheses of equality between the treatment and placebo effects will be tested using a mixed model, containing treatment group, week (as a classification term), and the interaction between treatment group and week as fixed effects; patient as random effect; and region and the common logarithm of the frequency of coughs per hour at baseline as covariates. In this model, the covariance structure will be given as unstructured, and the degrees of freedom will be derived using the Kenward-Roger method. Should the model fail to converge using the unstructured covariance, compound symmetry will be used. Using this model, the log-transformed ratio of the number of coughs per hour in 24 hours after 4 weeks of administration of study drug will be used to evaluate the null hypothesis at each dose level of S-600918 at the 2-sided alpha level of 0.05 among the FAS.

The primary analysis will summarize each of these three 2-way comparisons, presenting the estimate for the difference of the effects of treatment at Visit 6, the 95% confidence interval for this difference, and the p-value based on the hypothesis and model described above. Furthermore, the time course of the treatment effect for each treatment group will be plotted with the mean and 95% confidence interval.

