8.1.4. Other Analyses of the Primary Endpoint

Summary statistics for the average number of coughs per hour in 24 hours at each visit will be presented by treatment group using the geometric mean and its 95% confidence interval for the FAS.

Subgroup analyses will be performed to evaluate the primary efficacy endpoint among subgroups of patients for the FAS. For these subgroup analyses, the primary analysis method mentioned in the section 8.1.1 will be repeated. Within this framework, the subgroups below will be analyzed:

- 1. Region (1-1: Japan, Europe, United States, 1-2: Japan, Europe and United States)
- 2. Hourly cough count at baseline (≥30 coughs/hour, <30 coughs/hour)
- 3. Cough count at Visit 1 (≥30 coughs/hour, <30 coughs/hour)
- 4. Pulmonary/Cough History (Asthma, Cough variant asthma [CVA], Gastroesophageal reflux disease [GERD], Upper airway cough syndrome including postnasal drip, rhinosinusitis, and rhinitis [UACS], Eosinophilic bronchitis including atopic cough [EB], Sinobronchial syndrome [SBS], Unexplained cough, Other, and Refractory cough, i.e., other than Unexplained cough and Other). A patient may have more than one pulmonary history. Such patients will be included in each category by pulmonary history.

A forest plot will also be provided based on the estimates for the difference of the effects of treatment at Visit 6 and its 95% Confidence Interval for the subgroups above.

The primary analysis framework will be used to assess characteristics of the dose-response relationship on the primary efficacy endpoint. The framework will be applied as originally described as well as to the log-transformed ratio of average coughs per hour in 24 hours following 4 weeks of treatment to that at baseline. The below comparisons will be presented for each of these models.

- Placebo versus 50 mg, 150 mg, and 300 mg S-600918
- Placebo and 50 mg S-600918 versus 150 mg and 300 mg S-600918
- Placebo, 50 mg, and 150 mg S-600918 versus 300 mg S-600918
- Linear Trend Test across all Treatment Groups

This framework above will be applied to the log-transformed ratio of average coughs per hour in 24 hours following 3 weeks of treatment to that at baseline, as well.

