8.2.3. Analysis of Cough Severity (VAS)

The change in weekly cough severity at Visit 4, Visit 5, and Visit 6 to that at baseline will be analyzed using the primary analysis framework for the FAS. Similarly, the change in daily cough severity from Day 1 through Day 7 will be analyzed using the primary analysis framework for the FAS, only using Day 7 in place of Visit 6.

Both weekly and daily cough severity will also be summarized using descriptive statistics at each planned assessment by treatment group for the FAS.

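### If the unstructured fit fails, the single fallback to compound symmetry gives the tested visit an averaged variance, so the test can miss its 5% level in either direction

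*Protocol*

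**What the plan says.** The Synopsis (Statistical Methods, Efficacy Analyses) states: "The covariance structure will be determined to be unstructured". It does not say what happens if that fit fails.

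The body and the SAP do, and they agree. Protocol 9.10.3.1: "When the mixed model with unstructured covariance fails in convergence, compound symmetry will be applied as covariance structure". SAP 8.1.1: "Should the model fail to converge using the unstructured covariance, compound symmetry will be used". Neither lists an intermediate structure.

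On inference, SAP 8.1.1 says "the degrees of freedom will be derived using the Kenward-Roger method". Neither document names an empirical (sandwich) variance, so errors under the fallback are read here as model-based. The primary comparison is at one visit: the SAP describes "presenting the estimate for the difference of the effects of treatment at Visit 6".

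The rule reaches beyond the primary endpoint. For subgroups, SAP 8.1.4 says "the primary analysis method mentioned in the section 8.1.1 will be repeated"; these include nine cause-of-cough categories. SAP 8.2 says that only the response changes when the framework is reused. SAP 8.2.3 says "the change in daily cough severity from Day 1 through Day 7 will be analyzed using the primary analysis framework", with Day 7 as the tested day. ICIQ-SF and SF-36 have one post-baseline time point, so the fallback does not arise for them.

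**The concern.** Compound symmetry imposes one variance and one correlation on every visit. The hypothesis concerns only the last visit, so its standard error should rest on the variance at that visit. Under the fallback it rests on a pooled value from Weeks 1, 3 and 4, or from seven diary days. Kenward-Roger adjusts for small-sample uncertainty in the estimated covariance parameters; it does not repair a covariance of the wrong form.

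At stake is the width of the confidence interval and the p-value for each dose against placebo. The interval is too narrow if the tested visit is more variable than average, and too wide if it is less variable. A prespecified fallback is meant to keep the inference sound when the first choice fails. This one drops the visit-specific variance on which the Visit 6 test depends.

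**Working it through.** **1. The plan's own figure.** Protocol 9.2 and SAP 4.1 assume a difference of 0.163 and an SD of 0.371 on the log10 scale. The effect size is 0.163/0.371 = 0.439. The t-based calculation gives 83 per group (power 80.3%); 83/0.90 = 92.2, so 93; 4 × 93 = 372. The stated sample size is reproduced. The 0.371 is the only planning SD, with no values by visit.

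**2. Number of covariance parameters.** An unstructured matrix for k occasions has k(k+1)/2 parameters.
- Primary model, Visits 4, 5 and 6: 3 × 4/2 = 6.
- Diary, Days 1 to 7: 7 × 8/2 = 28.

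**3. Formula.** With complete data, compound symmetry estimates the common variance as the mean of the visit variances. Hence:
- r = SE under compound symmetry / true SE = √(mean visit variance / variance at tested visit)
- true two-sided level = 2 × [1 − Φ(1.96 × r)]

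Worked case, assumed SDs 0.297, 0.334 and 0.371 at Visits 4, 5 and 6: the variances are 0.0882, 0.1116 and 0.1376, with mean 0.1125. So r = √(0.1125/0.1376) = 0.904, 1.96 × 0.904 = 1.77, and the level is 7.6%.

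**4. Visit 6.** The SD is held at 0.371 at Visit 6; the other SDs are assumptions. The last two columns come from a REML simulation: 4 × 93 patients, within-patient correlation 0.6, random monotone dropout reaching 10% by Visit 6, 2,000 trials with three contrasts each, critical value 1.96.

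| SDs at Visits 4 / 5 / 6 | r | Level, formula | Level, simulated, model-based | Level, simulated, sandwich |
|---|---|---|---|---|
| 0.371 / 0.371 / 0.371 | 1.000 | 5.0% | 5.0% | 5.5% |
| 0.334 / 0.352 / 0.371 | 0.951 | 6.3% | 6.2% | 5.1% |
| 0.297 / 0.334 / 0.371 | 0.904 | 7.6% | 7.5% | 5.0% |
| 0.250 / 0.310 / 0.371 | 0.847 | 9.7% | 9.6% | 5.2% |
| 0.445 / 0.408 / 0.371 | 1.103 | 3.1% | 3.1% | 5.3% |
| 0.297 / 0.433 / 0.371 | 1.000 | 5.0% | 5.5% | 5.7% |

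In the third row the mean compound-symmetry SE is 0.0510 and the mean sandwich SE 0.0560, against an actual sampling SD of 0.0557. Nominal 95% intervals cover 92.4% in the third row and 90.3% in the fourth (formula). In the fifth row the test is conservative, and power at 83 per arm falls from 80.8% to 74.8% (normal approximation). In the last row the SDs differ, but the Visit 6 variance equals the average, so nothing is lost.

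**5. Day 7.** The SD is assumed to rise linearly over Days 1 to 7.

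| Day 1 SD as a share of Day 7 SD | r | Level |
|---|---|---|
| 100% | 1.00 | 5.0% |
| 80% | 0.90 | 7.7% |
| 75% | 0.88 | 8.5% |
| 60% | 0.81 | 11.2% |
| 50% | 0.77 | 13.2% |

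**6. Limit of the sandwich.** In complete-data simulations of small subgroups (relative SDs from 1, 1, 1 to 0.8, 0.9, 1), the uncorrected sandwich gave 9–12% error with 5 patients per arm, against 4–7% for model-based compound symmetry. With 8 per arm it gave 7–9% against 5–7%. From about 15 per arm the sandwich was better when SDs rose clearly.

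**The case against.** **The trigger is remote for the primary endpoint.** Six parameters with about 372 patients should converge. In simulated unstructured REML fits (4 × 93, 10% dropout plus 5% intermittent missingness) none of 200 failed, though with a purpose-written optimiser rather than SAS. This stands. One caveat is the wording "patient as random effect; and region and the common logarithm of the frequency of coughs per hour at baseline as covariates": a random patient effect fitted literally beside an unstructured matrix is over-parameterised and could itself cause failure.

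**The SD patterns are assumed.** This stands. Nothing in the documents shows that variability rises over visits or diary days, and with equal SDs the level is 5%.

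**A check already exists.** The ANCOVAs in SAP 8.1.2 use no repeated-measures covariance, so a distorted primary result could be compared with them. This stands in part: they are sensitivity analyses with single imputation, and they do not cover the diary.

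**The alternatives are imperfect.** Heterogeneous Toeplitz gives the 14-day gap (Day 8 to 22) and the 5-day gap (Day 22 to 27) the same correlation, and at three visits it saves one parameter (3 + 2 = 5 against 6). Heterogeneous compound symmetry has 3 + 1 = 4. This is true, but both keep a separate variance for the tested visit, which is what matters most here. For the diary they cut 28 parameters to 7 + 6 = 13 and 7 + 1 = 8.

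**Stakes.** This is a Phase 2b dose-selection trial with testing unadjusted for multiplicity. That limits the consequence but does not make the fallback correct.

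**Conclusion.** The point holds in conditional form. If the unstructured fit fails and the tested visit's variance differs from the average over visits, the fallback gives an interval of the wrong width. Under the assumed SD patterns the true two-sided error is about 3% to 10% at Visit 6 and 8% to 13% at Day 7. Non-convergence is unlikely for the primary model and more plausible for the 28-parameter diary model and the small cause-of-cough subgroups.

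A reader might infer three stronger things, none of which the documents support:
- That the synopsis contradicts the body. It only omits the fallback; the operative text is Protocol 9.10.3.1 and SAP 8.1.1.
- That the standard error is wrong whenever variability differs between visits. The last row of the Visit 6 table is a counterexample.
- That the primary test is expected to exceed 5%. That requires both a failed fit and a rising variance, and the documents give evidence of neither.

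The change is worth making because it is cheap. It should be made before unblinding, since choosing a structure afterwards would be post hoc.

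**What to change.** In Protocol 9.10.3.1 and SAP 8.1.1, replace the single fallback with an ordered list that keeps visit-specific variances, for example heterogeneous Toeplitz, then heterogeneous compound symmetry, with plain compound symmetry last. State that the list applies to every analysis using the primary framework, including SAP 8.1.4 and 8.2.3.

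Where a structured covariance is used in the full FAS or PPS, report empirical (sandwich) standard errors with a named degrees-of-freedom method. In small subgroups, keep model-based errors under the heterogeneous structure or use a small-sample-corrected sandwich. Align the synopsis with this wording. In the same edit, say whether patient enters only through the unstructured matrix.

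The cost is a few sentences and slightly more programming. Kenward-Roger must be replaced wherever the sandwich is used.
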